9.2. Informed Consent

A signed and dated ICF will be obtained from the patient as required by the protocol before any main screening procedures are conducted. A signed copy of the ICF will be given to the patient. Multiple ICFs covering different procedures will be required based upon local requirements.

9.3. Medical History

A complete medical history will be obtained during Screening within 28 days prior to first TAS-120 administration on Day 1 of Cycle 1.

Existing signs and symptoms will be obtained during screening (within 28 days prior to TAS-120 administration on Day 1 of Cycle 1), and reviewed on Day 1 of Cycle 1 (within 24 hours of dosing). If evaluation of signs and symptoms is performed during the screening period within 72 hours prior to dosing, the assessment does not need to be repeated on C1D1.

9.4. Physical Examination

A complete physical examination will be performed at the time points listed below.

- Screening (within 28 days prior to TAS-120 administration on Day 1 of Cycle 1).
- Within 24 hours prior to TAS-120 administration on Day 1 of each cycle. Note that procedures performed during the screening period within 72 hours prior to dosing do not need to be repeated on C1D1.
- At end of treatment (+0-7 days).
- 30-day safety follow-up visit.

9.5. Height, Vital Signs, and Weight

The patient's height will be obtained only during Screening within 28 days prior to TAS-120 administration on Day 1 of Cycle 1.

The patient's vital signs (blood pressure, heart rate, body temperature, and respiration rate) and body weight will be collected at the time points listed below. All vital signs are to be obtained with the patient in a position that is consistent for all time points for each patient.

- Screening (within 28 days prior to TAS-120 administration on Day 1 of Cycle 1).
- Within 24 hours prior to TAS-120 administration on Day 1 of each cycle. Note that procedures performed during the screening period within 72 hours prior to dosing do not need to be repeated on C1D1.
- At end of treatment (+0-7 days).
- 30-day safety follow-up visit.

9.6. Performance Status

An ECOG Performance Status score (see [Appendix C ECOG Performance Status](#)) will be obtained at the following time points:

- Screening (within 28 days prior to first TAS-120 administration on Day 1 of Cycle 1).
- Within 24 hours prior to TAS-120 administration on Day 1 of each cycle. Note that procedures performed during the screening period within 72 hours prior to dosing do not need to be repeated on C1D1.
- At end of treatment (+0-7 days).
- 30-day safety follow-up visit.

9.7. Electrocardiogram

A 12-lead resting ECG will be performed at the following time points:

- Screening (within 28 days prior to TAS-120 administration on Day 1 of Cycle 1).
- Two hours (\pm 15 min) after TAS-120 dose on Day 1 of Cycle 1.
- For all subsequent cycles starting with Cycle 2, ECG should be performed on Day 1 (\pm 3 days) of each cycle obtained 2 hours (\pm 15 min) after the TAS-120 dose.
- At end of treatment (+0-7 days).
- 30-day safety follow-up visit.

9.8. Ophthalmological Examination

Ophthalmological examination will be performed at the following time points:

- Screening within 28 days prior to TAS-120 administration on Day 1 of Cycle 1.
- 4-6 weeks after starting treatment with TAS-120
- Any other time due to local requirements, physician judgement and/or symptoms or signs of mineral deposits.
- At end of treatment (+0-7 days)
- 30-day safety follow-up visit.

The cornea and conjunctiva are readily visible tissues, and therefore, abnormalities of the cornea and conjunctiva can usually be recognized via external ocular examination and routine slit lamp biomicroscopy. The ophthalmologic examination will encompass the following:

1. External ocular examination.
2. Routine slit lamp biomicroscopy of anterior ocular structures (Fluorescein or rose Bengal or other dyes used to evaluate the ocular surface can be used according to institutional guidelines and local clinical practice).
3. Retinal exam to evaluate the anterior and posterior chamber

The examination will be repeated, if clinically indicated, and the repeat examination will include the same testing employed at Screening in addition to any other clinically indicated examination.

9.9. Neurological Examination

Neurological examination will be performed at the following time points for all patients:

- Screening (within 28 days prior to TAS-120 administration on Day 1 of Cycle 1).
- Any other time due to local requirements, physician judgement and/or symptoms or signs of mineral deposits.
- At end of treatment (+0-7 days)
- 30-day safety follow-up visit.

The basic neurologic examination should follow institutional guidelines and local clinical practice, and will encompass testing of:

- Cranial nerves II-XII.
- Muscular strength of upper and lower extremities.
- Deep tendon reflexes of upper and lower extremities.

This examination will be repeated, if clinically indicated, and the repeat examination will include the same testing employed at Screening in addition to any other clinically indicated examination.

9.9.1. Neurological Examination as part of RANO Evaluation for Patients with Primary CNS Tumors

For patients with primary CNS tumors, a complete neurological examination will include assessment of level of consciousness, mental status, speech, vision fundus (papilledema), cranial nerves III, IV, VI, cranial nerves other, motor, sensory, and gait or limb ataxia. An overall score according to a 6-point scoring code will be determined for each finding and recorded in the eCRF. Follow-up evaluation of the neurological examination will be based on any changes in the neurological clinical examination from the previous exam. Changes should be unrelated to postictal state or other unrelated events such as infection.

Neurological examination must always be performed at screening and within one week of the date of the Gd-MRI as part of the response assessment for patients with brain tumor.

Scoring code for each neurological finding:

- 0 = Normal
- 1 = Slightly or minimally abnormal
- 2 = Moderately abnormal
- 3 = Severely abnormal
- 4 = Grave
- 5 = Not able to record

Grading scale to designate relative changes:

- +2 = definitely better
- +1 = possible better

0 = unchanged

-1 = possible worse

-2 = definitely worse

9.10. Clinical Laboratory Evaluations

Blood samples for hematology, coagulation, and chemistry assessments will be collected and measured as described in [Section 9.10.1](#) and [Section 9.10.2](#), respectively. Laboratory assessments obtained prior to signing of the ICF may be used as screening laboratory values if they were obtained within 28 days prior to TAS-120 administration on Day 1 of Cycle 1.

All laboratory results must be reviewed for clinically significant events. Any clinically significant events must be followed and reported as required by the protocol (see [Section 11.1](#), Adverse Events/Serious Adverse Events and [Section 11.2](#), Laboratory Evaluations).

9.10.1. Hematology and Coagulation

Blood for hematology and coagulation assessments will be collected at the following time points and when clinically indicated:

- Screening (within 7 days prior to first TAS-120 administration on Day 1 of Cycle 1).
- Obtain within 24 hours before TAS-120 administration on Day 1 of each cycle, and anytime on Day 8 and Day 15 of Cycle 1. Note that procedures performed during the screening period within 72 hours prior to dosing do not need to be repeated on C1D1.
- At end of treatment (+0-7 days)
- 30-day safety follow-up visit.

In addition, the criteria for repeat testing listed in [Section 11.2.2](#), Repeat Testing, will be followed as needed.

The following hematology and coagulation parameters will be measured:

Red blood cell (RBC) count	White blood cell (WBC) count with differential
Hemoglobin	Neutrophils ¹
Hematocrit	Lymphocytes
Platelets	Monocytes
International normalized ratio (INR)	Eosinophils
Activated partial thromboplastin time (APTT)	Basophils

¹ Includes both segmented and band neutrophils.

9.10.2. Chemistry

Blood (serum or plasma) will be collected at the following time points for serum chemistry assessments:

- Screening (within 28 days prior to first TAS-120 administration on Day 1 of Cycle 1).
- Obtain within 24 hours before TAS-120 administration on Day 1 of each cycle, and anytime on Day 8 and Day 15 of Cycle 1. Note that procedures performed during the screening period within 72 hours prior to dosing do not need to be repeated on C1D1.
- Phosphorus is to be tested 4 days (± 24 hours) after Day 1 of Cycle 1 to initiate early intervention for hyperphosphatemia.
- As clinically indicated by the investigator or if previous chemistries showed an elevation of phosphorus that required action as specified in [Section 8.1.3.1.1](#).
- At the end of treatment (+0-7 days).
- 30-day safety follow-up visit.

In addition, the criteria for repeat testing listed in [Section 11.2.2](#), Repeat Testing, will be followed as needed.

The following chemistry parameters will be measured:

Table 11: Laboratory Assessments for TAS-120-101

Alanine aminotransferase (ALT)	Blood urea nitrogen (BUN) or Urea	Creatinine kinase (CK)
Aspartate aminotransferase (AST)	Phosphorus	Troponin I or T (quantitative) ^c
Alkaline phosphatase	Calcium	
Total bilirubin ^b	Chloride	
Glucose	Sodium	
Creatinine clearance ^a	Potassium	

^a Calculated (Ccr) or measured creatinine clearance.

^b Fractionation of bilirubin (= direct/indirect bilirubin or conjugated/unconjugated) must be performed/calculated in case of an elevation of total bilirubin.

^c Quantitative evaluation of either Troponin I or Troponin T (not both) required at each time point. Evaluation of the same parameter (Troponin I or Troponin T) at different timepoints for the same patient is not required.

9.10.3. Urinalysis

Urine samples for qualitative analysis (“urine dipstick”) will be collected at the time points listed below:

- Screening (within 28 days prior to first TAS-120 administration on Day 1 of Cycle 1).
- Within 24 hours prior to TAS-120 administration on Day 1 of each cycle. Note that procedures performed during the screening period within 72 hours prior to dosing do not need to be repeated on C1D1.
- At end of treatment (+0-7 days).
- 30-day safety follow-up visit.

In addition, the criteria for repeat testing listed in [Section 11.2.2](#), Repeat Testing, will be followed as needed. At all time-points, urinalysis should include:

- PH
- Specific gravity
- Protein
- Glucose
- Ketones
- Blood
- Leukocyte esterase
- Nitrite with microscopic examination if indicated

CCI

9.12. Pregnancy Test

For patients who are WOCBP, pregnancy testing by assessment of serum beta-human chorionic gonadotropin (β -HCG) will be conducted:

- At screening (28 days prior to the first administration of TAS-120); and
- At end of treatment (+0-7 days).

Serum or urine pregnancy test is also required:

- Within 24 hours prior to TAS-120 administration on Day 1 of each cycle, or additionally according to local requirements. Note that procedures performed during the screening period within 72 hours prior to dosing do not need to be repeated on C1D1.
- 30-day safety follow-up visit.

The date, time, and test results will be recorded in the patient's source documents.

Female patients who are not considered to be of child-bearing potential must have a history of being post-menopausal (no menses for 12 months without an alternative medical cause), surgical sterilization, or hysterectomy that is clearly documented in the patient's source documents.

9.13. Pharmacokinetic Sample Collection

9.13.1. Optional Pharmacokinetic Sample Collection for Phase 1 Expansion

For all patients in the Phase 1 Expansion, optional blood PK samples (a minimum of 1 mL) may be collected per the investigator's discretion in any patient at the following time points: prior to dosing (0 hour) and post-dose at 1, 2, 3, 4, 6, and 24 hours (\pm 10 minutes). The 24-hour post-dose sample should be collected prior to next TAS-120 administration. These optional blood PK samples could be collected on any day in Cycle 1 and Cycle 2 when PK should be collected as part of the safety evaluation.

For patients in the Phase I Expansion with primary CNS tumors only, optional blood and CSF samples will be collected 2-4 hours post-dose on Day 1 of Cycle 2 to assess the TAS-120 concentration ratio of CSF to plasma. Blood and CSF samples must be collected at the same time point (within 15 minutes). A minimum of 1 mL each of whole blood and CSF will be collected for the PK analysis.

Blood and CSF samples for PK evaluation will be collected and processed according to instructions provided in the Laboratory Manual.

9.13.2. Pharmacokinetic Blood Sample Collection for Phase 1 Expansion/Phase 2

During Phase 1 Expansion and Phase 2, blood samples of TAS-120 will be collected on Day 1 of Cycle 2 pre-dose, 1 h \pm 30 min. and 3 h \pm 30 min. post-dose to assess the plasma exposure at 20 mg QD. In addition, blood samples will be collected on Day 1 of Cycle 3 and Cycle 4 pre-dose. A minimum of 1 mL of whole blood will be collected for the PK analysis per [Table 12](#). The total blood volume collected for the PK samples will be approximately 5 mL per patient.

Blood samples for PK evaluation will be collected and processed according to instructions provided in the Laboratory Manual.

Table 12: Pharmacokinetic Blood Sample Collection for Phase 1 Expansion CCI

Day of Study	Collection Time Point (hours [h]) in Relation to TAS-120 Administration (Time Window)	Blood Volume
Day 1 of Cycle 2	pre-dose	1 mL
	1 h ± 30 min post-dose	1 mL
	3 h ± 30 min post-dose	1 mL
Day 1 of Cycle 3	pre-dose	1 mL
Day 1 of Cycle 4	pre-dose	1 mL
Total volume per patient		Approximately 5 mL
h = hour		

9.14. ctDNA Analysis of FGF/FGFR Aberrations

9.14.1. ctDNA from Blood Sample for the Analysis of FGF/FGFR Aberrations

For the Phase 1 Expansion and Phase 2, a blood sample will be collected to assess FGF/FGFR aberrations in ctDNA at Screening within 28 days prior to the first TAS-120 administration on Day 1 of Cycle 1 (required) and at the EOT visit (optional). A minimum of 20 mL of whole blood will be collected at each time point. This sample is being collected for exploratory analysis to evaluate FGF/FGFR aberrations in circulating blood and for future clinical development. Sample collection and preparation will be according to instructions provided in the Laboratory Manual.

9.15. Prior and Concomitant Medications and Therapies

All therapies and medications, prescription and over-the-counter, will be collected from the time the main study ICF is signed through the 30-day safety follow-up visit, including any medication used to treat AEs or SAEs during the 30-day follow-up period. Use of concomitant medication and/or therapy should be documented in the patient's source documents. In addition, the time of initiation of new anticancer therapy received during the 30-day follow-up period will be collected.

9.16. Adverse Event Assessment

Patients will be monitored for any untoward medical events (AEs or SAEs) from the time the main study ICF is signed through 30 days after last dose of TAS-120 or until the start of new antitumor therapy, whichever is earlier. For the Phase 2 part of the study, any AEs or SAEs that occur after the signing of pre-screening consent and are directly associated with a pre-screening procedure (i.e., fresh tumor biopsy) should be reported as described in Section 12.1. For AEs and SAEs that occur between signing the pre-screening consent and main study ICF, there is no need to record those that are unrelated unless it is mandatory by local regulations.

Serious AEs should be reported to Taiho Oncology, Incorporated (TOI) Pharmacovigilance or its designee. If serious medical occurrences or deaths **outside** the 30-day follow-up period are

reported to or observed by the investigator that he/she believes are related to the administration of the TAS-120, it is the investigator's responsibility to report this occurrence to TOI Pharmacovigilance or its designee. See [Section 11.1.1](#), Adverse Events, and [Section 11.1.2](#), Serious Adverse Events, for definitions and detailed reporting of AEs and SAEs.

9.17. Tumor Assessments/Scans

9.17.1. Tumor Assessment for Advanced Solid Tumors

Tumor assessments/imaging studies of the chest, abdomen, and pelvis (as clinically indicated) must be obtained at each time point listed below for all patients with solid tumors.

- Screening within 28 days prior to Day 1 of Cycle 1. Computed tomography scans obtained prior to the signed ICF may be used as the screening scan if they were obtained within 28 days of the first dose of TAS-120.
- At the end of every 2 cycles (up to +2 weeks), up to Cycle 4.
- Following Cycle 4, at least after every 3 cycles (\pm 7 days) or as clinically indicated, until documented progression (including after end of treatment if the patient discontinues for reasons other than radiologic disease progression).
- At end of treatment (+0-7 days), a CT scan must be performed if the prior scan was performed \geq 9 weeks prior to discontinuation of TAS-120 treatment if the patient discontinued for reasons other than radiologic disease progression.

On-site tumor assessments will be performed by the investigator/local radiologist according to RECIST guidelines (version 1.1, 2009). Results of these assessments, including response for target and non-target lesions and appearance of new lesions, will be the basis for the continuation or discontinuation of TAS-120. Response definitions are provided in [Section 10](#), Efficacy Assessment Criteria.

If the investigator determines that a patient has developed clinical progression manifested by symptomatic deterioration but not supported by radiologic evidence of progression, the patient should stop treatment. Symptoms of clinical progression must be documented in the patient's source documents and must be reported as AEs. Every effort should be made to document objective progression even after discontinuation of treatment.

The same method of assessment and the same technique must be used to characterize each identified and reported lesion at Screening, throughout the study, and during the follow-up period.

On-site tumor assessments will be conducted. Tumor assessment scans from patients with iCCA treated at 16, 20 and 24 mg QD and patients with primary brain tumors may also be prospectively or retrospectively collected and forwarded to the core imaging laboratory.

If a patient in Phase 1 Expansion or Phase 2 has a response, response confirmation should be obtained through tumor assessments/scans 4 to 6 weeks after the first documentation of response. Patients must then return to their original schedule of assessments (i.e., every 2 cycles [or every 3 cycles after Cycle 4]).

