PRO (EQ-5D and EORTC QLQ-C30)		X					X			Evaluated at screening and as close as possible to the tumor assessment schedule: at the end of every 2 cycles (up to +2 weeks) through Cycle 4 and every 3 cycles (± 7 days) thereafter until disease progression or initiation of new anticancer therapy (whichever is first).	
Tumor assessments / scans		X					X		(X)	
Same tumor assessments/scans obtained at screening at the end of every 2 cycles (up to +2 weeks) up to Cycle 4. Thereafter tumor assessments may be performed every 3 cycles (± 7 days), or as clinically indicated, until radiologic PD or initiation of new anticancer therapy (whichever occurs first).
 
At EOT, tumor assessment must be performed if the prior scan was performed ≥ 9 weeks prior to discontinuation of treatment if the patient discontinued for reasons other than radiologic disease progression. See also Section 9.17.
 
After EOT, patients who discontinued for reasons other than radiologic disease progression should continue to receive tumor assessments every 3 cycles (± 7 days), or as clinically indicated, until radiologic disease progression or initiation of new anticancer therapy (whichever occurs first).
	

	Pre-Screening	Screening Period (Within 28 Days Prior to First Dose)	Treatment Period (1 cycle = 21 days)				Safety Follow-up		Survival Follow-up Period	Notes
			Cycle 1			Cycles ≥ 2	End of Tx (+0-7 days)	30 (± 3) days After Last		
			Day 1	Day 4 ($\pm 1d$)	Day 8 ($\pm 3d$)	Day 15 ($\pm 3d$)				
Survival status								X	After discontinuation of treatment, survival follow-up should occur every 3 months (± 2 weeks) for up to 18 months after last patient enrolled in the Phase 2 portion of the study.	
TAS-120 Dosing			—————→							Patients are required to fast for ≥ 2 hours before and 1 hour after each administration of TAS-120; patients are permitted to drink water. TAS-120 should be administered in the morning or evening, at the same time (if possible) each day. See Section 8.1.1.

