7.3.1. End of Treatment Discontinuation Criteria

The reason for discontinuation should be documented in the source documents.

Patients can be withdrawn from treatment for the following reasons:

- At the patient's request at any time irrespective of the reason.
- RECIST-defined disease progression of solid tumors or RANO-defined disease progression of brain tumors.
- Clinical progression.
- Unacceptable adverse events (AEs), or change in underlying condition such that the patient can no longer tolerate therapy, as evidenced by:
 - A dose delay > 21 days from the scheduled start date of the next cycle.
 - Need for more than the allowed dose reductions of TAS-120 as described in [Section 8.1.3.1](#), TAS-120 Dose Reductions for Treatment-emergent Toxicities.
- Physician's decision including need for other anticancer therapy not specified in the protocol, or surgery or radiotherapy to the only site(s) of disease being evaluated in this protocol.
- Pregnancy.

Upon discontinuation of treatment the investigator is to ensure the following:

- The Clinical Research Associate (CRA) must be notified immediately; and
- The Study Treatment Discontinuation Form in the electronic case report form (eCRF) must be completed, specifying the primary reason for the patient's withdrawal from the study.

If there is strong evidence of clinical benefit and reasons to justify continuation of TAS-120 dosing even though treatment discontinuation criteria have been met, this decision must be reviewed with the sponsor on a case-by-case basis, and continuation of therapy may be allowed assuming all other treatment resumption criteria have been met. Post-study provisions are provided in [Section 13.4](#).

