8.1.2. Treatment Regimen

TAS-120 will be administered as a daily, continuous, 21-day treatment cycle until at least 1 of the criteria for study discontinuation is met. TAS-120 must be administered as outlined in Study Drug Administration ([Section 8.1.1](#)) and Dose Reduction/Modification Procedures ([Section 8.1.3](#)). There are no breaks in dosing between cycles.

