If the toxicities requiring dose reduction as defined above do not recover based on the criteria defined in [Table 6](#) through [Table 8](#) within the 21 days of the last dose of TAS-120, the patient

will be discontinued permanently from the study. If resumption criteria are met within 21 days of the last dose of TAS-120, the patient can resume TAS-120 treatment at the appropriate dose level according to instructions provided in [Section 9.1.3.1](#), TAS-120 Dose Reductions for Treatment-emergent Toxicities.

Treatment-emergent toxicities should be followed until stabilization according to [Table 9](#).

Table 9: Required Follow-up for Toxicities

Toxicity	Follow-up evaluation
Hematology	If \geq CTCAE grade 3 neutropenia or \geq CTCAE grade 3 thrombocytopenia have been demonstrated, these parameters must be repeated at least twice a week until resolution to \leq CTCAE grade 1 or baseline to allow for initiation of re-treatment, and then at least weekly until either initiation of retreatment or until stabilization.
Renal	If creatinine clearance (calculated* or measured value**) < 30 mL/min has been demonstrated, this parameter must be repeated at least twice a week until resolution to baseline to allow for initiation of re-treatment, and then at least weekly until either initiation of re-treatment or until stabilization.
Hepatic	If bilirubin ≥ 2 x ULN or \geq CTCAE grade 3 ALT or AST or the combination of \geq CTCAE grade 2 bilirubin and \geq CTCAE grade 2 ALT or AST elevation has been demonstrated, these parameters must be repeated at least twice a week until resolution to \leq CTCAE grade 1 or baseline to allow for initiation of re-treatment, and then at least weekly until either initiation of re-treatment or until stabilization. Patients with total bilirubin $> 1.5 \times$ ULN, or > 3.0 mg/dL for patients with Gilbert's syndrome (any duration) should have fractionation of bilirubin into total/direct or indirect/direct components and any additional work-up as clinically indicated by these results. Follow-up of hyperbilirubinemia should proceed as per the guidelines above, irrespective of the results of fractionation.

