12.2.2.4. Progression-free Survival

Progression-free survival (PFS) is defined as the time from the day of the first dose to the date of first objectively documented disease progression or death (any cause), whichever occurs first. Patients who die without a reported disease progression will be considered to have progressed on the date of their death. Patients who did not progress or die will be censored on the date of their last tumor assessment. Patients who did not have any on-study assessments and did not die will be censored on the first dosing date. Patients who started any subsequent anti-cancer therapy without a prior reported progression will be censored at the last tumor assessment prior to initiation of the subsequent anti-cancer therapy. Early progression rate (EPR) for the GBM or Grade III glioma cohort will be assessed as the progression-free rate at the end of Cycle 2.

Progression-free survival will also be analyzed as a time-to-event endpoint with the median (Kaplan-Meier estimate) and associated 95% CI (Brookmeyer-Crowley methodology) reported, along with the Kaplan-Meier estimates for PFS rates at 3, 6, 9 and 12 months and associated 95% CIs (log-log transformation methodology of Kalbfleisch-Prentice).

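### Tumour scans are counted in treatment cycles, with no calendar anchor at first dose, so a dose hold may move scan dates and modestly distort the secondary PFS estimates

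*Protocol*

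**What the plan says.** Protocol 9.17.1 places scans "At the end of every 2 cycles (up to +2 weeks), up to Cycle 4", and after that at least every 3 cycles "or as clinically indicated, until documented progression". Responders return to the same cycle-based schedule after their confirmation scan. The Phase 2 SAP repeats the scheme in its Table 1.

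On cycle length, protocol 8.1.2 says "TAS-120 will be administered as a daily, continuous, 21-day treatment cycle" and "There are no breaks in dosing between cycles". Yet 7.3.1 lists as evidence of intolerable toxicity "A dose delay > 21 days from the scheduled start date of the next cycle", so a shorter slip of the next cycle is tolerated. Section 8.1.3.1.2 has another 21-day limit, counted differently: recovery "within the 21 days of the last dose of TAS-120".

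After treatment ends, the schedule tables still count in cycles: "After EOT, patients who discontinued for reasons other than radiologic disease progression should continue to receive tumor assessments every 3 cycles".

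PFS and DOR end at documented progression, which in practice is the date of the detecting scan, or at death. Section 12.2.2.4 asks for "Kaplan-Meier estimates for PFS rates at 3, 6, 9 and 12 months". In the Phase 2 SAP, Table 6 row 7 censors a progression or death found after two or more missed assessments at the last scan before the gap. Footnote d defines that gap as longer than 2 cycles in the first 6 months and longer than 3 thereafter.

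**The concern.** If a dose hold pushes back Day 1 of the next cycle, and sites count scans in cycles as written, the scan moves back as well. Patients with more toxicity would then be scanned later in calendar time than patients dosed without interruption, and their progression would be found later for a reason unrelated to the disease. The design has one arm, so no comparator absorbs the effect. The absolute PFS figures are what a reader would set against the historical second-line median of 3.2 months cited in protocol 5.1. The 3- and 9-month landmarks look especially exposed because a nominal scan falls just before each.

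**Working it through.** **1. The plan's own figure.** The Phase 2 SAP (6.4.1) requires at least 17 responders of 100 for the Clopper-Pearson 95% lower bound to exceed 10%. The bound is the 2.5% quantile of Beta(r, 100 − r + 1): 10.23% for r = 17 and 9.43% for r = 16, so 17 is reproduced. The rule counts responders and does not use a progression date.

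**2. Scan gaps.** Inputs: 21-day cycles (8.1.2); windows of +14 days to Cycle 4 and ±7 days later (9.17.1); tolerated slip of 21 days (7.3.1).

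| Interval | Nominal | One 21-day slip | One slip plus window | Every cycle start in the interval slips, plus window |
|---|---|---|---|---|
| Cycles 1–2 | 42 d = 6 wk | 63 d = 9 wk | 77 d = 11 wk | 77 d = 11 wk |
| Cycles 3–4 | 42 d = 6 wk | 63 d = 9 wk | 77 d = 11 wk | 42 + 42 + 14 = 98 d = 14 wk |
| Cycles 5–7 | 63 d = 9 wk | 84 d = 12 wk | 91 d = 13 wk | 63 + 63 + 7 = 133 d = 19 wk |

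**3. Landmarks.** At 30.4375 days per month, 3 months is Day 91.3 and 9 months is Day 273.9. The nominal Cycle 4 scan is Day 84 and the Cycle 13 scan is Day 273. A cumulative slip of 8 days (84 + 8 = 92) or 1 day (273 + 1 = 274) carries them past. With no slip at all, however, the windows already allow Days 84–98 and 266–280, which straddle both landmarks.

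**4. PFS with scans exactly on schedule, row 7 not applied.** The documents give no delay rates, so these are assumptions: exponential progression times and a fixed probability that each cycle start is late. Selected results, 60,000 simulated patients per row:

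| True median (months) | Delay | Kaplan-Meier median | 6-month PFS | 9-month PFS |
|---|---|---|---|---|
| 3.2 | none | 4.83 | 35.1% | 14.2% |
| 3.2 | 7 d in 20% | 4.83 | 33.2% | 19.9% |
| 3.2 | 21 d in 20% | 4.83 | 36.9% | 17.5% |
| 6 | none | 6.90 | 57.1% | 35.6% |
| 6 | 7 d in 20% | 7.13 | 55.4% | 42.3% |
| 6 | 21 d in 20% | 7.59 | 58.3% | 39.4% |
| 9 | none | 11.04 | 68.9% | 50.1% |
| 9 | 7 d in 20% | 9.66 | 67.5% | 56.3% |
| 9 | 21 d in 20% | 10.35 | 69.6% | 53.8% |

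The 9-month rate rises by 3.3 to 6.7 points in these rows, and the 6-month rate moves by −1.9 to +1.8. At a true median of 6 months, mean lag from true to detected progression rises from 29.5 days to 31.6 and 36.2. Across delays of 7–21 days in 5–20% of cycle starts, the rise is about 0.5–7 days for true medians of 4–6 months. The 3-month rate is unchanged with 7 days in 5%, rises by under 1 point with 7 days in 20%, and by 3.5–7 points with 21 days in 20%.

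The median falls in the 9-month case for a simple reason. At Day 273 survival is 2^(−273/273.9) = 0.501, so without delays the curve just misses 50% there and the median jumps to the next scan, Day 336 (11.04 months). Delays scatter scans between those days, and the curve crosses 50% earlier.

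**5. PFS with windows.** With scans spread uniformly over the permitted windows, the same delays move the 3- and 9-month rates by only about 0–3 points. The windows alone add about 3–6 points at 3 months and about 4 at 9 months.

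**6. DOR.** With 21-day delays in 20% of cycles, true median DOR of 6 or 9 months and an assumed median of 8 weeks to response, mean DOR goes from 9.74 to 9.97 months and from 14.00 to 14.27. The medians (7.59 and 10.35) are unchanged. Delays confined to the early cycles leave the mean within 0.02 month, because the onset of response is also found late; the median was then 6.90 against 7.59 in the 6-month case.

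**7. SAP row 7.** Read as calendar limits of 42 and 63 days, row 7 censors many delayed progressions: 53–57% with 21-day delays in 20% of cycles, against 12–20% with none. The Kaplan-Meier median then goes from 6.90 to 8.28, 8.97 to 13.80 and 13.11 to 20.70 months (true 3.2, 6 and 9). The no-delay share arises because the planned gap from Day 84 to Day 147 is 63 days, already above 42. At a true median of 6 months (182.6 days) it is 2^(−84/182.6) − 2^(−147/182.6) = 0.727 − 0.572 = 15.5%, against 15.6% simulated.

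**The case against.** The best reply is that the mechanism is inferred. Section 8.1.2 describes continuous dosing, the schedule tables define a cycle as 21 days, and missed doses are not replaced (8.2.4). On that reading a hold does not stretch a cycle, and the post-treatment schedule simply means every 63 days. Some toxicities are also managed first without a hold: Grade 3 phosphorus by dose reduction (Table 7), Grade 3 neutropenia at the same dose (Table 8). Scans may be done earlier when clinically indicated, and an end-of-treatment scan is required if the last was at least 9 weeks before. The design has one arm and the affected endpoints are secondary.

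Much of this stands. The post-treatment wording is a weak complaint by itself, and the delay rates are not the plan's. What remains is that 7.3.1 speaks of a next cycle starting late, which sits badly with a cycle that cannot slip, and no text tells a site which count governs the scan.

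A reader might infer more: that dose delays lengthen PFS and DOR. The documents do not support that. They never say that a hold moves the scan date. Even if it does, median PFS can fall, the DOR median did not rise, and row 7 may censor a late progression instead of dating it late. Nor is the sensitivity at 3 and 9 months mainly due to delays, since the windows alone contribute as much or more.

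**Conclusion.** The point holds as a gap in the schedule with a modest effect. Scan timing depends on a cycle count that the protocol lets slip in one section and describes as unbroken in another, so patients can be assessed on different calendars according to drug exposure. The 3- and 9-month PFS rates could be overstated by up to about 6–7 points with scans exactly on schedule, or about 0–3 points with the permitted windows. Mean DOR rises by at most about 0.2–0.3 month in the cases run. The ORR rule is not shown to change.

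These sizes rest on exponential event times, on assumed delay rates, and on a hold moving the scan count. The direction and size under SAP row 7 cannot be settled until its limits are defined as calendar or actual cycles.

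**What to change.** In protocol 9.17.1, Tables 1 and 2 and the SAP copies, give scan due dates as the end of Weeks 6 and 12 and then every 9 weeks from first dose, with the planned windows. State that holds and delayed cycles do not move these dates, and that the same calendar continues after end of treatment until radiologic progression or new anticancer therapy. The opening of Section 9 allows ±2 weeks up to Cycle 4 where 9.17.1 allows only +2 weeks, so the two must be made to agree.

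In Phase 2 SAP Table 6, footnote d, write the missed-assessment limits in calendar days consistent with that schedule, so that an on-time 9-week gap does not count as missed scans.

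Sections 7.3.1, 8.1.2 and 8.1.3.1.2 should also be reconciled on whether and how a cycle start can slip; this point takes no position on which rule is right.

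The cost is a few sentences and no extra scans under nominal dosing. The one downside is that after a delay a scan may not coincide with a Day 1 visit. The windows will still leave some spread around the 3- and 9-month landmarks.
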